2.4.2 Sensitivity analyses for the on-treatment estimand

To investigate missing not at random scenarios, a tipping point analysis of the hypothesis that IDeg is superior to IGlar 300 U/mL will be performed for the on-treatment estimand. In this analysis the event rates for subjects that discontinued randomised treatment in the IDeg OD arm during either titration or maintenance 1 periods is gradually increased until the difference between the two treatments is no longer statistically significantly different. If the penalty found by this method is evaluated to be clinically plausible the sensitivity analysis does not support the primary analysis. If the penalty is not considered plausible the sensitivity analysis supports the primary analysis.

To investigate the potential influence of subjects with high number of events, the analysis of the ontreatment estimand will be repeated on data where the maximal number of events in maintenance 2 is truncated at three. The value three is based on data from SWITCH 2 (NN1250-3998) where three hypos correspond to the 95% percentile in the IDeg arm. Furthermore, a statistical sensitivity analysis is performed with a truncation at seven, to accommodate for the longer analysis period in the current trial (36 weeks instead of 16 weeks).

The primary analysis will be performed using only available on-treatment data during maintenance 2. Subjects without on-treatment data for maintenance 2 period will be excluded from this analysis, and thus no imputation is needed.

The primary analysis will be repeated, but considering the full maintenance period (maintenance 1 and maintenance 2). Missing data will be imputed for subjects that discontinued randomised treatment during titration period only, using on-treatment data for maintenance 1 and 2. This

Statistical Analysis Plan Trial ID: NN1250-4252 UTN: U1111-1184-8175 EudraCT No.: 2016-002801-20	CONFIDENTIAL	Date: Version: Status: Page:	12 March 2019 3.0 Final 14 of 31	Novo Nordisk
---	--------------	---------------------------------------	---	--------------

analysis evaluates if including the data from the discontinued BG-meter challenge the overall conclusion of the trial.

The primary analysis will be repeated, with the exemption of imputation of hypoglycaemic episodes for subjects in IDeg arm actively refusing to reconsent to the extended trial period following the protocol amendment, defined as subjects discontinuing treatment after 15FEB2018 and either not reconsenting or not taking any doses of trial product later than the date of reconsenting. For these subjects, the imputation will be based on the usual statistical model fitted to all maintenance 2 data in the IGlar arm. This analysis evaluates if the conclusion of the primary analysis is different if non-consenters on IDeg arm are worse off than consenters.

The impact of protocol deviations and outliers may be investigated further in sensitivity analyses.

2.4.3 Statistical analysis for the ITT estimand

The ITT estimand will be estimated based on information from maintenance 2 collected regardless of whether subjects used randomised treatment or not, i.e. including data after premature discontinuation.

Missing data for withdrawn subjects prior to maintenance 2 will be imputed based on off-treatment data from the same arm from maintenance 2. The imputations and the analysis will be made using the same method as for the on-treatment estimand. If the imputation model cannot fit or leads to inflate the standard error of the treatment ratio on logscale by more than 15% compared to a negative binomial model fitted to the available on- and off-treatment data during maintenance 2 without any imputation the analysis will not be performed.

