17.4.3 Statistical analysis for the secondary estimand

The secondary estimand will be estimated based on information from maintenance 2 collected regardless of whether subjects used randomised treatment or not, i.e. including data after premature discontinuation.

Missing data for withdrawn subjects will be imputed based on off-treatment data from the same arm from maintenance 2 for subjects that discontinued randomised treatment during maintenance 2. The imputations and the analysis will be made using the same method as for the primary estimand.

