2.4 Primary endpoint

2.4.1 Primary statistical analysis for the on-treatment estimand

The on-treatment estimand will be estimated based on information from maintenance 2 collected when subjects use randomised treatment including a 7-day follow-up period (on-treatment data). Subjects that discontinue randomised treatment during maintenance 2 will contribute with the available on treatment data from maintenance 2. For subjects that discontinue randomised treatment during the titration period or maintenance 1, the number of events in maintenance 2 will be imputed based on data from the same arm from maintenance 2 for subjects that discontinued randomised treatment during maintenance 2. Missing data within each group will be imputed as follows:

- First 1000 samples from the posterior distribution of model parameters will be extracted. The model will be fitted to the on-treatment maintenance 2 data for subjects that discontinued randomised treatment during maintenance 2. This will be done using a Bayes Poisson log-link model dosing time as a factor, age as covariate, and log of exposure time as offset.
- For each sample of model parameters, the total number of hypoglycaemia events for subjects that discontinued randomised treatment in the titration period or maintenance 1 will be imputed as a random number of events from a Poisson distribution using the sampled parameters.

CONFIDENTIAL

Date: Version: Status: Page: 12 March 2019 Novo Nordisk 3.0 Final 13 of 31

Having 1000 complete data sets that have maintenance 2 data for all randomised subjects, the mean treatment ratio will be estimated using a negative binomial model with all the factors described in section 2.1, age as covariate and log exposure time as offset. The estimates and standard deviations will be pooled to one estimate and associated standard deviation using Rubin's formula. From these the 95% confidence intervals for the treatment ratio and the associated p-value will be calculated.

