2.4.4 Sensitivity analysis for the ITT estimand

A tipping point sensitivity analysis similar to the one for the on-treatment estimand will be performed. The penalty will only be added to withdrawn subjects in IDeg arm. Further sensitivity analyses may be performed.

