Trial ID: NN1250-4252 CONFIDENTIAL Version: 3.0 UTN: U1111-1184-8175 CONFIDENTIAL Version: 3.0 EudraCT No.: 2016-002801-20 Page: 17 of 31	Statistical Analysis Plan Trial ID: NN1250-4252 UTN: U1111-1184-8175 EudraCT No.: 2016-002801-20	CONFIDENTIAL	Date: Version: Status: Page:	12 March 2019 3.0 Final 17 of 31	Novo Nordisk
---	---	--------------	---------------------------------------	---	--------------

For both periods, hypoglycaemic episodes during the 7 days treatment-emergent period after last drug day will be included.

The number of severe or BG confirmed symptomatic hypoglycaemic events during total treatment period (up to 88 weeks) will be analysed statistically, addressing both the on-treatment and ITT estimand. Also nocturnal severe or BG confirmed symptomatic hypoglycaemic events as well as severe hypoglycaemic events during total treatment period will be analysed following these procedures.

The on-treatment estimand is estimated based on on-treatment data and a negative binomial model including the factors in section 2.1, age as covariate and the logarithm of the time period in which a hypoglycaemic episode was considered treatment emergent as offset. The model will use log as link function.

The ITT estimand is based on in-trial data. For withdrawn subjects, data after withdrawal will be imputed for a period lasting from the day after withdrawal up until 36 weeks after entering maintenance 2 period, and until 36 weeks after first reconsent of any subject in trial (i.e. until 09NOV2018) for subjects not entering maintenance 2. The imputation will follow the procedure described in section 2.4.1, using all off-treatment data to build the imputation model. Observed and imputed data are summarised by subject, and analysed through a negative binomial model including the factors in section 2.1, age as covariate and the logarithm of the total time period where hypoglycaemic episodes are either observed or imputed as offset. The model will use log as link function. If the imputation model cannot fit or leads to inflate the standard error of the treatment ratio on logscale by more than 15% compared to a negative binomial model fitted to the available on- and off-treatment data during total treatment period without any imputation the analysis will not be performed.

Body weight

Body weight (absolute value and change from baseline) will be summarised descriptively by visit.

Statistical Analysis Plan
Trial ID: NN1250-4252
UTN: U1111-1184-8175

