3.10 Omitting backup strategy for ITT estimand

After p 86 l. 2100 the following is added:

Statistical Analysis Plan Trial ID: NN1250-4252	CONFIDENTIAL
UTN: U1111-1184-8175	CONTIDENTIAL
EudraCT No.: 2016-002801-20	

Date: Version: Status: Page:

"If the imputation model cannot fit or leads to inflate the standard error of the treatment ratio on logscale by more than 15% compared to a negative binomial model fitted to the available on- and off-treatment data during maintenance 2 without any imputation the analysis will not be performed."

Rationale:

For ITT estimand it is not appropriate to include on-treatment data in the imputation model, and the statistical analysis is thus omitted if the imputations model is deemed unstable.

3.11 Sensitivity analyses for primary analysis ITT estimand:

p. 8512101:

"The same sensitivity analysis as the sensitivity analyses for the on-treatment estimand will be performed."

is replaced by

"A tipping point sensitivity analysis similar to the one for the on-treatment estimand will be performed. The penalty will only be added to withdrawn subjects in IDeg arm. Further sensitivity analyses may be performed."

Rationale: The sensitivity analysis addressing missing data patterns is considered the primary sensitivity analysis, other sensitivity analysis will be performed if necessary.

3.12 Clarification of primary analysis ITT estimand:

p 86 l. 2116: the following is deleted:

"for subjects that discontinued randomised treatment during maintenance 2"

Rationale:

Not intended statement in original protocol, as we want to impute base on all available off-treatment data.

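### SAP 2.4.3 imputes only subjects withdrawn before maintenance 2, so withdrawals during maintenance 2 enter the ITT analysis on observed time alone, unlike the SAP's own total-period ITT analysis

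*SAP*

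**What the plan says.** SAP 2.4.3 sets who is imputed for the ITT estimand: "Missing data for withdrawn subjects prior to maintenance 2 will be imputed based on off-treatment data from the same arm from maintenance 2". It then adds: "The imputations and the analysis will be made using the same method as for the on-treatment estimand".

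That method is in SAP 2.4.1. It imputes subjects who stopped early: "For subjects that discontinue randomised treatment during the titration period or maintenance 1, the number of events in maintenance 2 will be imputed". Later stoppers are not imputed: "Subjects that discontinue randomised treatment during maintenance 2 will contribute with the available on treatment data from maintenance 2". The analysis model is negative binomial with log exposure time as offset.

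Protocol version 3.0, section 17.4.3, covers the same analysis without a time limit: "Missing data for withdrawn subjects will be imputed based on off-treatment data from the same arm from maintenance 2". It too says that the method is that of the primary estimand.

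SAP 2.6.2, on the ITT analysis of the total treatment period, says: "For withdrawn subjects, data after withdrawal will be imputed for a period lasting from the day after withdrawal up until 36 weeks" after entry to maintenance 2. Observed and imputed counts are then summed over the full period.

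SAP 2.4.4 describes the ITT tipping-point analysis: "The penalty will only be added to withdrawn subjects in IDeg arm".

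SAP 3.12, which revises the ITT analysis, lists only a deletion concerning which subjects supply the off-treatment data. The words restricting imputation to withdrawals before maintenance 2 appear in no entry of section 3.

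**The concern.** The ITT estimand is defined regardless of adherence. Protocol 6.5 reserves withdrawal for subjects who decline all further contact, so nothing is observed afterwards. A subject who leaves in week 10 of the 36 weeks enters with about 10 weeks of offset and no counts for the other 26. The model then treats the missing weeks as missing at random given the fitted rates. That suits an on-treatment estimand. It does not suit a treatment-policy estimand, because most subjects who leave the trial are likely to stop trial insulin as well.

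The ITT analysis is there to show whether the on-treatment result survives non-adherence. A rule that pulls it towards the on-treatment result weakens that check. The rule also reaches the nocturnal and severe endpoints, which SAP 2.5.1 analyses in the same way. The same subject would be imputed in the total-period analysis but not in the maintenance 2 analysis.

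**Working it through.** **Plan figure first.** The current documents give no power for the ITT estimand, so I checked the on-treatment one. Inputs from SAP 2.2: adjusted ratio 0.765, IDeg rate 1.8 per patient-year, dispersion 3.1, 805 per arm, 36 weeks.

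- SE² = [(1/1.8 + 0.765/1.8)/(36/52) + 2 × 3.1]/805 = (1.416 + 6.2)/805 = 0.00946, so SE = 0.0973.
- |ln 0.765|/SE − 1.96 = 0.268/0.0973 − 1.96 = 0.79, which gives power 78.6% against the stated 79%. The plan's rate model is reproduced.

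**What the offset implies.** In a gamma-Poisson model the implied rate for unseen time mixes the subject's own rate with the model mean. The weight on the own rate is m/(1/3.1 + m), with m = rate × weeks/52. For rates of 1.8 and 2.4 it is:

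| Weeks observed | Own-rate weight |
|---|---|
| 4 | 0.30 to 0.36 |
| 18 | 0.66 to 0.72 |
| 27 | 0.74 to 0.79 |

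No off-treatment data enter. I take exposure time to mean observed in-trial time in maintenance 2, because 2.4.3 does not redefine it.

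**Size, equal withdrawal.** Plan rates are 1.8 on IDeg and 1.8/0.75 = 2.4 on IGlar. Assumptions, none of them from the documents' current text:

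- A share w of each arm withdraws during maintenance 2, from treatment and half-way on average, so the lost fraction is f = w/2.
- Withdrawers have the same underlying risk as other subjects.
- After withdrawal both arms have a common rate r of 1.8 to 3.6.
- The 9% end is the superseded version 2.0 figure of 13% not completing on treatment, less 4% lost before maintenance. It is an upper bound, since it counts subjects who stop treatment but stay in the trial.

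Target ratio = [1.8(1 − f) + rf]/[2.4(1 − f) + rf]. The rule as written keeps 0.750.

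| w | r = 1.8 | r = 2.4 | r = 3.6 |
|---|---|---|---|
| 2% | 0.752 | 0.753 | 0.754 |
| 5% | 0.755 | 0.756 | 0.759 |
| 9% | 0.759 | 0.761 | 0.767 |

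Example, w = 9% and r = 3.6: (1.719 + 0.162)/(2.292 + 0.162) = 1.881/2.454 = 0.767.

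A large-sample simulation with dispersion fixed at 3.1 and r = 2.4 gave shifts of 0.002, 0.007 and 0.011 at 2%, 5% and 9%, in line with the middle column.

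**Size, unequal withdrawal, r = 3.6.**

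| IDeg / IGlar | Target ratio |
|---|---|
| 6% / 3% | 1.854/2.418 = 0.767 |
| 3% / 6% | 1.827/2.436 = 0.750 |
| 3% / 9% | 1.827/2.454 = 0.7445 |

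So the direction depends on the balance of withdrawal. At r = 3.6 the shift vanishes when IGlar withdrawal is twice that of IDeg, and reverses beyond that.

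**The case against.** The strongest reply concerns the protocol. Its 17.4.3 also says that the primary estimand's method applies, and that method imputes only subjects who stopped before maintenance 2. On that reading the SAP merely makes explicit what was meant, and section 3 says it omits linguistic updates. This stands in part. The method sentence can be read as saying how to impute, while the sentence before it says for whom, but the text is ambiguous. A reader might infer a proven undeclared departure from the protocol; the documents do not go that far.

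A reader might also infer that SAP 3.10 contradicts 2.4.3, since it states: "For ITT estimand it is not appropriate to include on-treatment data in the imputation model". That passage explains why the backup strategy is dropped and concerns the data used to fit the imputation model. Subjects who are not imputed bring no on-treatment data into it. Nor does 2.4.4 contradict 2.4.3. It is modelled on the on-treatment tipping analysis, which penalises only subjects who stopped in titration or maintenance 1. What remains is a knock-on gap: nothing says how the penalty reaches withdrawals during maintenance 2.

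Finally, describing the missing weeks as extrapolated at each subject's own, mostly on-treatment, rate would be too strong. The implied rate is shrunk towards the model mean. A subject who entered maintenance 2 off treatment at V57A and then withdrew contributes off-treatment data only, and no split is given.

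The difference from 2.6.2 survives all of this. That analysis covers a longer period, but the period includes the same weeks of the same subjects, and the SAP gives no reason for treating them differently.

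**Conclusion.** The point holds as an inconsistency within the SAP and a poor fit to the ITT estimand. Under the equal-withdrawal assumptions the target is 0.752 to 0.767 against 0.750. SAP 3.7 reports few treatment discontinuations during maintenance 2, which points to the low end, a shift of about 0.002 to 0.004.

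A reader might take the top of the range, about 0.017, as the expected error. It needs both the 9% upper bound and an off-treatment rate twice the planned IDeg rate, and nothing in the documents supports that combination. A reader might also infer that the rule always favours IDeg. Over the assumed range it does so when withdrawal is equal or higher on IDeg, but not when it is sufficiently higher on IGlar and the off-treatment rate is high.

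The confirmatory hierarchy uses the on-treatment estimand, so no confirmatory conclusion changes. The correction should still be made, because this is the secondary estimand for the primary endpoint and the change is small.

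**What to change.** In SAP 2.4.3, delete the words *prior to maintenance 2*. For a subject who withdraws during maintenance 2, impute from the day after withdrawal to 36 weeks after V57/V57A, using same-arm off-treatment maintenance 2 data. Add observed and imputed counts and use the full-period offset, as 2.6.2 already does. State in 2.4.4 that the penalty applies to these imputed counts, and list the revision in section 3.

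The cost is a few sentences and reuse of code already needed for 2.6.2. Imputation variance rises somewhat, and so does the chance of exceeding the 15% standard-error limit, at which 2.4.3 drops the analysis. SAP 3.7 shows that sparse data made the protocol's imputation model unstable, so this risk is real. If the limit is exceeded, report the available-data analysis in its place.

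If the sponsor prefers to keep the restriction, the minimum is to list it in section 3 and justify the difference from 2.6.2.

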2.4.4 Sensitivity analysis for the ITT estimand

A tipping point sensitivity analysis similar to the one for the on-treatment estimand will be performed. The penalty will only be added to withdrawn subjects in IDeg arm. Further sensitivity analyses may be performed.

2.5 Secondary endpoints

2.5.1 Confirmatory secondary endpoints

Provided that IDeg OD is superior to IGlar 300 U/mL OD for the primary endpoint using the ontreatment estimand, the confirmatory secondary endpoints will be tested for superiority of IDeg OD over IGlar 300 U/mL OD using the on-treatment estimand.

The confirmatory secondary endpoints are given below; the order of the endpoints defines the testing sequence. The hierarchical testing strategy will control the family wise type 1 error in the strong sense at 5% (two sided).

Trial ID: NN1250-4252 CONFIDENTIAL Version: 3.0 UTN: U1111-1184-8175 Status: Final EndraCT No : 2016-002801-20 Page: 15 of 31	Statistical Analysis Plan Trial ID: NN1250-4252 UTN: U1111-1184-8175 EudraCT No : 2016-002801-20	CONFIDENTIAL	Date: Version: Status: Page:	12 March 2019 3.0 Final 15 of 31	Novo Nordisk
---	---	--------------	---------------------------------------	---	--------------

- 1. Basal insulin dose (U) at end of maintenance 2 (up to 88 weeks)
- 2. Number of nocturnal, severe or BG confirmed symptomatic hypoglycaemic episodes during maintenance 2 (36 weeks)
- 3. Number of severe hypoglycaemic episodes during maintenance 2 (36 weeks)

The hypoglycaemic endpoints will be analysed with the same analysis method as the primary endpoint including backup strategy and with similar sensitivity analysis.

Basal insulin dose at end of maintenance 2 will be analysed as follows: A basal insulin dose at every titration, maintenance and end of treatment visit mentioned in the flow chart will be calculated as a mean of the insulin doses in the 7 day period before the visits. For the on-treatment estimand these doses will be analysed on log-scale with an MMRM with the factors described in section 2.1 and age at baseline and logarithm of pre-trial insulin dose as covariate, all nested within visit. If this model does not converge visits and/or factors will be excluded from the analysis. Before transforming to log-scale, dose values of 0 will be assigned the value 0.5.

Insulin dose will also be analysed with the ITT estimand, i.e. including insulin dose collected after premature discontinuation. This is done using a pattern mixture model using multiple imputation to handle missing data. Imputation of missing data at end of trial will be done within the 4 groups of subjects defined by randomised treatment and whether subjects discontinued randomised treatment or not. Missing data within each group will be imputed as follows:

- An analysis of covariance model for insulin dose at visit 93 and 93A with the factors listen in 2.1 (except treatment) and pre-trial insulin dose and age at baseline as covariates will be fitted to the observed data.
- The estimated parameters will be used to impute 1000 values for insulin dose at visit 93/93A, creating 1000 complete datasets.

Having 1000 complete datasets, each of these will be analysed using an analysis of covariance model with all the factors listed in 2.1, pre-trial insulin dose and age at baseline as covariates. The estimates and standard deviations will be pooled to one estimate and associated standard deviation using Rubin's formula. From these the 95% confidence intervals for the treatment ratio and the associated p-value will be calculated.

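### The supplementary ITT imputation of insulin dose uses none of the subject's own on-trial doses, at a small cost in precision and in protection against dose-related missingness

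*SAP*

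**What the plan says.** SAP 2.5.1 has two analyses of basal insulin dose, the first confirmatory secondary endpoint.

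- **On-treatment estimand.** At each visit a dose is "calculated as a mean of the insulin doses in the 7 day period before the visits". One repeated-measures model then takes all of these visit doses, so every one of them contributes: "For the on-treatment estimand these doses will be analysed on log-scale with an MMRM". This is the analysis in the hierarchy: "the confirmatory secondary endpoints will be tested for superiority of IDeg OD over IGlar 300 U/mL OD using the on-treatment estimand".
- **ITT estimand.** This additional analysis uses multiple imputation, done "within the 4 groups of subjects defined by randomised treatment and whether subjects discontinued randomised treatment or not". The ANCOVA for the V93/V93A dose has the section 2.1 factors without treatment, "and pre-trial insulin dose and age at baseline as covariates will be fitted to the observed data". In the second step the fitted model supplies the missing end doses: "The estimated parameters will be used to impute 1000 values for insulin dose at visit 93/93A". Each completed data set is analysed with an ANCOVA on baseline variables. No visit dose between randomisation and V93/V93A appears in either step.

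Two other places bear on who lacks an end dose. Under Protocol 8.1.9, subjects who discontinue treatment but stay in the trial have their basal insulin dose recorded at V93A. Under Protocol 8.1.6 and 8.1.7, subjects who do not re-consent finish at V54 and its two follow-up visits, so their schedule contains neither V93 nor V93A. For the confirmatory secondary endpoints, SAP 2.5.1 names sensitivity analyses only for hypoglycaemia.

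**The concern.** In a treat-to-target trial the pre-trial dose is a dose of a different insulin, and the trial dose is then adjusted weekly towards a glucose target. The dose a subject had reached before leaving probably says more about the later requirement than the pre-trial dose does. The ITT model discards it.

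Two things are at stake. One is precision. The other is the credibility of missing at random: within a discontinued group, those who stayed until V93A supply the model and those who left receive its predictions. If leavers had been titrated to higher or lower doses than stayers with the same baseline, the model cannot tell. The trial is open-label, so such a pattern could differ by arm. The on-treatment and ITT dose results might then differ because of the imputation model and not because of the estimand.

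**Working it through.** **1. The plan's own figure.** SAP 2.2 gives 805 per arm, adjusted ratio 0.906, CV 0.65, one-sided 2.5% and power 92%.

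- Log-scale SD = sqrt(ln(1 + 0.65²)) = 0.594.
- SE = 0.594 × sqrt(2/805) = 0.0296.
- Power = Φ(0.0987/0.0296 − 1.96) = 91.6%.

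The 92% reproduces. Nothing in it depends on the ITT imputation.

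**2. Inputs for the size.** The documents give no missing share for the ITT dose analysis and no correlation between visit doses. Assumed ranges:

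- Share discontinuing, p: 6% is what the adjusted ratio implies, (0.906 − 0.90)/(1 − 0.90) = 0.06, although the text of SAP 2.2 says 4%. 13% is the figure in section 17.2 of the superseded protocol version 2.0 for subjects not completing on treatment; it serves only as an upper value.
- Share of discontinuers without an end dose, m: about half (0.5, or 6/13 = 0.46), and 0.75 as a poor case.
- R²: the share of the variance left after the baseline covariates that the last titrated dose explains, 0.25 to 0.8.

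**3. Precision.** With imputation by group and random missingness, the variance relative to complete data is 1 + p × m/(1 − m) × (1 − R²). The planned model corresponds to R² = 0.

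| p | m | SE factor, planned model | SE factor with titrated dose (R² 0.25 to 0.8) | Excess SE of planned model |
|---|---|---|---|---|
| 0.06 | 0.50 | 1.030 | 1.022 to 1.006 | 0.7% to 2.3% |
| 0.13 | 0.46 | 1.054 | 1.041 to 1.011 | 1.3% to 4.3% |
| 0.13 | 0.75 | 1.179 | 1.137 to 1.038 | 3.7% to 13.6% |

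**4. Bias.** Suppose missingness among discontinuers depends on titrated dose in one arm only. The shift in the log ratio is about p × m × Δ × ρ × s. Here s = 0.594 × sqrt(1 − 0.7²) = 0.424 is the SD left after a pre-trial dose with assumed correlation 0.7. ρ is the partial correlation of titrated with end dose. Δ is the difference in titrated dose between missing and retrieved subjects, in SDs. A log-odds of 1 per SD gives Δ = 0.83.

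- p = 0.13, m = 0.46, ρ = 0.7: 0.13 × 0.46 × 0.83 × 0.7 × 0.424 = 0.0147; ratio 0.906 × exp(−0.0147) = 0.893.
- p = 0.06, m = 0.5, ρ = 0.7: 0.0074; ratio 0.899.
- p = 0.13, m = 0.46, ρ = 0.7, log-odds 0.3 per SD (Δ = 0.29): 0.0052; ratio 0.901.

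A simulation with 805 per arm, true ratio 0.906, p = 0.13 and imputation of discontinuers within arm (300 trials, 30 imputations, Monte Carlo error about 0.001) agrees:

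| Missingness among discontinuers | Planned model | With last titrated dose |
|---|---|---|
| Same dependence in both arms, m = 0.46, ρ = 0.7 | 0.906 | 0.906 |
| One arm only, m = 0.46, ρ = 0.7 | 0.893 | 0.907 |
| One arm only, m = 0.46, ρ = 0.9 | 0.891 | 0.908 |
| One arm only, m = 0.75, ρ = 0.7 | 0.886 | 0.906 |

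In these cases the bias favours IDeg; with the dependence reversed it would favour the comparator.

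**The case against.** Imputation from retrieved dropouts on baseline covariates is a legitimate choice, and it matches the covariates of the analysis ANCOVA. Several stronger readings are tempting, and the documents do not support them.

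- A reader might infer that discontinuation is ignored. It is not: the four groups carry it, and an average difference between discontinuers and completers comes through the doses recorded at V93A.
- A reader might infer bias whenever leavers had higher or lower doses. That is not enough. Leavers must differ from retrieved subjects in the same group beyond the baseline covariates, and must do so differently by arm. The same pattern in both arms cancels in the ratio.
- A reader might infer a threat to the confirmatory claim. The hierarchy uses the on-treatment MMRM, which already includes all visit doses.
- A reader might infer that the planned intervals are too wide in absolute terms. They are wider only relative to a richer model. If the estimated parameters are held fixed without posterior draws, which the SAP leaves open, intervals could be too narrow: in the m = 0.75 case the mean SE was 0.0222 against an empirical 0.0242.

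Two objections limit the gain. Discontinuers move to NPH and then to a marketed product (Protocol 5.4), so their V93A dose is of another regimen and the correlation may be weaker than assumed. For someone stopping early in titration, the last dose is still close to the starting dose. Also, SAP 3.7 reports unstable imputation from few maintenance 2 discontinuers (for event counts), so an extra parameter in small groups is a real cost. Both points shrink the benefit; neither is a reason to discard the doses altogether.

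**Conclusion.** The point holds as a minor improvement to a supplementary analysis. On-trial doses that the plan already derives are left out of the ITT imputation model. The excess SE is about 1% to 4% at 6% to 13% discontinuation with about half of discontinuers missing, and reaches 13.6% only if three quarters are missing and the titrated dose is highly predictive. Bias of about 1.5% to 2% in the ratio needs dose-related missingness that differs by arm, at the upper discontinuation share and with a strong dependence; with weaker inputs it is below 1%. All of these sizes rest on assumed correlations and missing shares. Non-re-consenters have no scheduled V93/V93A dose, so the missing share among discontinuers could be high, but the documents do not give it.

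**What to change.** In step 1 of the ITT imputation in SAP 2.5.1, keep the four groups and add the log of one on-trial 7-day mean dose, always taken before the outcome visit:

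- in the two discontinued groups, the dose at the last on-treatment visit;
- in the two non-discontinued groups, the dose at a fixed earlier visit that both observed and missing subjects have.

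The V93 dose itself must never be the covariate. For a completer, the last available on-treatment dose is the V93 dose, and the regression would then predict the outcome from itself.

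Put the outcome on the log scale; SAP 2.5.1 states this only for the MMRM, although the ITT analysis also reports a ratio. Fall back to the current model when a group is too small or a subject has no on-trial dose. The analysis ANCOVA keeps its present terms.

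The cost is one covariate, already derived for the MMRM. The downside is one more parameter in small discontinued groups, and a smaller gain there because the V93A dose is of a later product.
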